**IV. Protocol**

Among Veteran smokers with chronic moderate to severe pain, a pain intensity  $\geq 4$  for 3 or more months, we are proposing a randomized comparative effectiveness trial to compare the effectiveness of a telephone-based smoking cessation intervention including CBI for pain to a standard telephone-based smoking cessation intervention. The goals of the study are: 1) Evaluate the impact of **smoking cessation plus CBI (SMK-CBI)** on cigarette abstinence rates among Veterans with chronic pain at 6 and 12-months compared to **standard smoking cessation counseling (SMK-STD)**; 2) Evaluate the impact of **SMK-CBI** on pain intensity and pain interference among Veterans at 6- and 12-months compared to **SMK-STD**; 3) Assess whether change in self-efficacy and pain-related anxiety mediate the impact of **SMK-CBI** on smoking cessation in Veterans with pain at 6- and 12-months compared to **SMK-STD**.

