## V. Outcomes:

Participants will be surveyed three times: enrollment, 6-months post-intervention and 12-months post-intervention using VA RED Cap to collect these data. Baseline survey will assess demographics, smoking history, nicotine dependence, global self-efficacy to quit smoking, depression, pain intensity and other covariates related to pain and smoking, via telephone. Follow-up surveys will be administered at 6-months and 12 months post-intervention. The follow-up surveys will assess smoking status, pain intensity, use of intervention materials (e.g., NRT, PASS activity booklet), and intervention acceptability (e.g., intervention appropriateness, suitability, effectiveness, and convenience). Participants will be compensated \$25 per completed follow-up survey. We will abide by the patient's preference since many patients may be reluctant to send their sensitive bank information or provide it over the phone for this telephone-based study.

Saliva samples will be collected from participants who report not smoking in the last 7 days (7-day point prevalence) in order to biochemically validate their self-reported smoking status. This process has been shown to improve the validity of self-reported smoking cessation. Samples will be collected at next clinic visit following the telephone interview. Saliva samples will measure cotinine levels using NicAlert dipsticks with a standard cut point of 16 ng/ml to determine abstinence. Participants will receive \$10 incentive for providing each saliva sample.

Counseling session fidelity will be assessed using audio-taped recordings of sessions. We aim to record approximately 20% of sessions (all sessions in the first 3 months of the study and then one week every 2 months for the remainder of the study). Investigators will rate 10% of the sessions to ensure protocol fidelity and lack of drift of information from the SMK-CBI to SMK-STD over time.

**Outcome 1: Prolonged abstinence:** In keeping with the SNRT recommendations for measuring abstinence, we will use prolonged abstinence as our main outcome and allow for a grace period around quit date. During the 6- and 12-month follow-ups, patients will be asked about prolonged abstinence, "In the past 6 months, have

you smoked at least a part of a cigarette on each of 7 consecutive days?" and "In the past 6 months, have you smoked any cigarettes in each of 2 consecutive weeks?"

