**Outcome 2: Point prevalent abstinence:** At each follow-up (6-and 12-month), patients will be asked whether they have smoked a cigarette, even a puff, in the past 7 days and, if no, will be asked whether they have smoked a cigarette, even a puff, in the past 30 days.

**Outcome 3: Pain intensity (usual) and pain related functional interference:** Participants will complete the BPI, which includes 2 multi-item scales measuring pain intensity and pain-related functional interference. Pain intensity in the past 24 hours is measured in 4 items—worst, least, current and usual—each using a validated 11-point *numerical rating scale* (0-10). A rating of 0 indicates no pain while 10 indicates the worst pain imaginable. A score of 4 or above is considered a clinically significant pain level according to VHA treatment guidelines. The functional interference subscale consists of 7 items measuring self-rated pain interference related to general activity, mood, walking ability, normal work (inside or outside the home), relations with other people, sleep and enjoyment of life. Respondents rate how much pain has interfered with these aspects of their lives in the past 24 hours on a 0 (does not interfere) to 10 (completely interferes) point scale.

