### **Analyses**

**Hypothesis 1.1:** Prolonged abstinence rates will be significantly higher among Veterans in the SMK-CBI group compared to those in the SMK-STD group.

**Hypothesis 1.2:** The 7-day point prevalence abstinence rates will be significantly higher among Veterans in the SMK-CBI group compared to those in the SMK-STD group.

Rates of cigarette abstinence (prolonged abstinence) will be assessed at 6- and 12-month follow-up. Abstinence will be measured as a dichotomous variable that indicates whether patients have been abstinent or not. The same analysis approach will be used to test both prolonged and 7-day point prevalence abstinence rates. Self-report of abstinence will be validated with cotinine saliva testing.

We will use logistic regression to test for a between-group difference in abstinence rates at 6 months. This logistic regression model can be written as:  $\text{Logit}(\pi_i) = \beta_0 + \text{SMK-CBI}_i * \beta_1$ , where  $\pi_i$  represents the probability that patient  $i$  has abstained from smoking at the 6-month follow-up. In this model, SMK-CBI $_i$  is the intervention group indicator; therefore,  $\beta_1$  represents the log-odds ratio of smoking abstinence in the SMK-CBI group as compared to the SMK-STD group. For each of the abstinence outcomes, we will formally evaluate the intervention effect by testing that  $\beta_1$  differs from zero and report the odds ratio ( $\exp(\beta_1)$ ) and 95% CI of the odds ratio. An odds ratio significantly greater than 1.0 provides evidence that SMK-CBI group patients have higher prolonged abstinence rates. The model will also include stratification variables (gender) as recommended in the CPMP guidelines.

Sustainability, or longer term effects of the intervention, will be examined by comparing abstinence rates between groups at 12 months. We will model change in abstinence rates at baseline, 6, and 12 months using generalized linear models with a logit link fit with generalized estimating equations. The regression coefficients from this model have essentially the same interpretation as those from a cross-sectional regression analysis (e.g. logistic regression) but are more appropriate as they properly incorporate the within-subject correlation that is inherent in the longitudinal structure of the data. The model will be fit using the SAS procedure GENMOD (SAS Institute, Cary, NC).

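### The 12-month abstinence GEE names baseline as an outcome time although abstinence is asked only at 6 and 12 months, and no model term delivers the 12-month comparison

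*Combined protocol and SAP*

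**What the plan says.** All references are to the combined protocol and SAP.

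- **VI. Statistical Protocol, Analyses (Hypotheses 1.1 and 1.2), longitudinal model:** "We will model change in abstinence rates at baseline, 6, and 12 months using generalized linear models with a logit link", fitted by GEE in SAS GENMOD.
- **Same section, timing of the outcome:** "Rates of cigarette abstinence (prolonged abstinence) will be assessed at 6- and 12-month follow-up".
- **Same section, purpose of the longitudinal analysis:** sustainability "will be examined by comparing abstinence rates between groups at 12 months".
- **V. Outcomes, Outcome 1:** "During the 6- and 12-month follow-ups, patients will be asked about prolonged abstinence". One of the two items is "In the past 6 months, have you smoked any cigarettes in each of 2 consecutive weeks", a look-back over six months.
- **V. Outcomes, Outcome 2:** "At each follow-up (6-and 12-month), patients will be asked whether they have smoked a cigarette".
- **V. Outcomes, baseline content:** "Baseline survey will assess demographics, smoking history, nicotine dependence, global self-efficacy to quit smoking, depression, pain intensity", followed by an open-ended reference to further covariates. Smoking status is listed only for the follow-up surveys.
- **IV. Protocol and 6. Research Plan:** the population is described as "Among Veteran smokers with chronic moderate to severe pain", and eligibility requires current tobacco use.

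The 6-month logistic model is written as an equation with a named test coefficient and is to include gender. The pain models under Hypothesis 2.1 name time-by-treatment interactions. The abstinence GEE has no equation, time coding, group-by-time term, working correlation or named contrast. The plan says only that its coefficients can be read much like those of a cross-sectional regression.

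**The concern.** The longitudinal model needs an outcome at three times, and the plan collects it at two. A change from baseline cannot be modelled as worded, because the baseline value is either absent or fixed near zero by the entry criteria.

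This GEE is the only stated analysis of the 12-month abstinence comparison. That comparison is part of the first study goal, and the model serves both prolonged and 7-day point prevalence abstinence. The analyst will have to decide what to do with baseline, how to code time, whether to include group-by-time, and which coefficient or contrast is the 12-month result. Some of these choices return the 12-month odds ratio. Others return a mixture of the 6- and 12-month effects. The difference matters when an effect fades or emerges after 6 months, which is the question a sustainability analysis is meant to answer.

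**Working it through.** The documents supplied give no abstinence rates, so there is no figure of the plan's to reproduce. All rates below are assumptions, written SMK-CBI/SMK-STD.

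**Step 1. Times.** The model uses baseline, 6 and 12 months. Both abstinence outcomes are asked at 6 and 12 months. The baseline outcome has no listed source.

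**Step 2. If baseline is not collected.** The model reduces to 6 and 12 months, and there is no change from baseline to estimate.

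**Step 3. If baseline is set from eligibility.**
- *Exactly 0 in an arm:* logit(0) = ln(0/1), which is minus infinity, so terms referenced to baseline have no finite estimate. A categorical-time fit to expected proportions with zero at baseline gave an intercept of about −27.6 and standard errors of about 18,600 to 26,300.
- *A few non-cigarette tobacco users counted as abstinent:* assume 371 + 100 = 471 participants split 236/235. The chance of no abstainers in at least one arm is 1 − (1 − 0.99^236)(1 − 0.99^235) = 18% at a true 1%, and 1.7% at a true 2%. With one abstainer per arm, the baseline log odds ratio has SE √(1/1 + 1/235 + 1/1 + 1/234) = 1.42.

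**Step 4. Does the baseline row damage the 12-month contrast?** Not with categorical time, group-by-time and a contrast at 12 months. In simulated data with zero baseline, the 12-month log odds ratio differed from the fit on 6 and 12 months alone by 0.000 (independence) or at most 0.015 (exchangeable).

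**Step 5. Other codings the text allows.** These are large-sample fits with independence working correlation, equal arms and no gender term. The true odds ratio for 20/12 is (0.20/0.80)/(0.12/0.88) = 1.83.

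*(a) Assigned zeros, linear time, group-by-time.* In each arm the fitted probabilities m at t = 0, 1, 2 (units of 6 months) satisfy Σm = Σp and Σt·m = Σt·p. For 20/12 then 12/12:
- SMK-CBI: m = 0.0519, 0.0963, 0.1719 (sum 0.32; weighted sum 0.44).
- SMK-STD: m = 0.0274, 0.0652, 0.1474 (sum 0.24; weighted sum 0.36).
- Fitted 12-month OR = (0.1719/0.8281)/(0.1474/0.8526) = 1.20, against a true 1.00.

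*(b) Single group effect, 6 and 12 months only.* Without a time term this is the odds ratio of the averaged rates. For 20/12 then 12/12 these are 16% and 12%: (0.16/0.84)/(0.12/0.88) = 1.40. Adding categorical time leaves it at 1.40. The table gives the version with categorical time.

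| Assumed rates (%), 6 then 12 months | True 12-month OR | 6/12 only, categorical time, group-by-time | (a) | (b) |
|---|---|---|---|---|
| 20/12 then 12/12 | 1.00 | 1.00 | 1.20 | 1.40 |
| 22/12 then 10/10 | 1.00 | 1.00 | 1.29 | 1.55 |
| 20/12 then 16/12 | 1.40 | 1.40 | 1.52 | 1.61 |
| 12/12 then 20/12 | 1.83 | 1.83 | 1.66 | 1.40 |
| 20/12 at both | 1.83 | 1.83 | 1.88 | 1.83 |
| 12/12 at both | 1.00 | 1.00 | 1.00 | 1.00 |

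The model on 6 and 12 months with group-by-time reproduces each cell, so its 12-month odds ratio is exact. Coding (b) has no baseline row, yet in every row where the effect changes between visits it is further from the truth than (a).

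**The case against.** The strongest defence is that the intent is clear and the baseline wording is close to harmless. The plan says in words that groups will be compared at 12 months. A competent analyst would probably use categorical time, include the interaction and report that contrast, and the baseline rows would then not matter. The distortions in the table need codings that the plan does not state, and an effect that changes between visits. With no effect at either visit nothing is distorted. All of this stands, and it limits the size of the point.

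Four stronger readings are tempting, and the documents do not support them.

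- *That the 12-month comparison is not specified at all.* It is stated in words; only the model term is missing.
- *That the baseline row by itself biases the 12-month result, or that deleting it is enough.* Step 4 shows that the row need not bias anything. Coding (b) shows that harm remains without it if group-by-time is left out.
- *That baseline abstinence is certainly never recorded.* The baseline survey list is open-ended, so for point prevalence this is an inference. For prolonged abstinence, the questions are placed at the follow-ups.
- *That the planned software will fail.* The divergence in step 3 comes from other code. It shows that the baseline terms have no finite estimate, not how GENMOD will behave.

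The defence does not remove the conflict over assessment times, and it relies on the analyst supplying terms that the plan leaves out.

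**Conclusion.** The sentence is wrong as written and should be corrected. Naming baseline as an outcome time conflicts with the assessment schedule in V. Outcomes and with the Analyses section itself, and a logit-scale change from an all-zero baseline cannot be estimated. This part follows from the documents and needs no assumed rates, apart from the reading that baseline abstinence is uncollected or about zero.

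The practical risk lies more in the missing group-by-time term and contrast than in the baseline row. Under the assumed rates, a vanished effect (true 12-month odds ratio 1.00) could be reported as 1.20 to 1.55 across the two scenarios. A late effect (true 1.83) could be reported as 1.66 or 1.40. A sustained effect is barely altered (1.83 against 1.88 at most). These sizes rest on assumed rates, large samples and independence working correlation.

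The 6-month logistic test is unaffected. So is the condition for running the mediation analysis under Hypothesis 3.1, which depends on that 6-month model. The point merits correction but does not threaten the main 6-month analysis.

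**What to change.** Delete baseline as an outcome time and replace the longitudinal sentence with wording such as:

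> Abstinence at 6 and 12 months will be analysed with a logit-link marginal model fitted by GEE with robust standard errors, including group, categorical time (6, 12 months), group-by-time and gender. The test of sustainability is the group contrast at 12 months, reported as an odds ratio with 95% CI. The same model applies to prolonged and to 7-day point prevalence abstinence.

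The working correlation should be named, but the choice can be left to the sponsor's statistician; with two visits, exchangeable and unstructured are the same.

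The cost is a change of SAP wording. It needs no new data and does not change the 6-month test.

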## VI. Statistical Protocol:

**Data Summary.** Descriptive statistics, including graphical displays, will be used to summarize all study variables, both overall and by intervention group. Evidence of imbalance in baseline characteristics will be noted and discussed as to whether they are clinically significant. As recommended by Committee for Proprietary Medicinal Products (CPMP) guidelines, we will consider sensitivity analyses adjusting for these baseline characteristics to ensure that an observed intervention effect is not due to this baseline imbalance. We will construct individual and mean trajectory plots of the longitudinal outcome variables (e.g., BPI) to understand their general trends over the study period. In addition, we will explore the variability and correlation structure of the longitudinal outcome variables. All statistical analyses will be performed using the SAS software package; the VACHS Center of Innovation maintains the current SAS release on our system.

**Intent-to-Treat Analysis.** All primary and secondary analyses focus on the effect of SMK-CBI as compared to SMK-STD. We, therefore, plan to use the intent-to-treat assumption for all analyses; participants will be analyzed as part of the group to which they are randomized, regardless of intervention adherence.

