**Hypothesis 2.1:** Veterans in the SMK-CBI will report significantly lower usual pain intensity and pain interference compared to the SMK-STD group.

We will use linear mixed effects models procedure for analyzing repeated measures data with fixed and random effects to evaluate study group assignment effects on our continuous and repeated outcomes (pain intensity and pain interference). The Mixed Models procedure is designed for unbalanced repeated measures with missing data, allowing for intra-participant serial correlation and unequal variance and covariance structure across time. It provides tests of the overall between-participant effects, repeated measures (time) effects, tests of fixed and random effects, and analysis of reduced models that can provide detailed tests of specific pattern of results. A repeated measures analysis of variance in the Mixed Models procedure takes into consideration differences that may emerge over time; we will use this procedure to test for a significant effect of the two treatments on the primary outcome measure, time, and the interactions between time and each of the two treatments. Random effects will also be included to account for intra-participant correlation of repeated measures. Additionally, the model will include the stratification variables. We plan to estimate the parameters in the model using the SAS procedure MIXED (SAS Version 9.2, Cary, NC).

**Hypothesis 3.1:** The relationship between pain-related anxiety intervention and smoking cessation will be mediated by self-efficacy and pain-related anxiety.

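### The Hypothesis 2.1 pain model leaves out enrollment BPI and names no deciding contrast, so the comparison of arms on pain is unbiased but less precise than its baseline-adjusted version.

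*Combined protocol and SAP*

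**What the plan says.** The second study goal (IV. Protocol) is the effect of SMK-CBI "on pain intensity and pain interference among Veterans at 6- and 12-months compared to" SMK-STD. It names both time points and ranks neither.

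Under Hypothesis 2.1 (VI. Statistical Protocol, Analyses) the mixed model is used to "test for a significant effect of the two treatments on the primary outcome measure, time, and the interactions between time" and each treatment. Random effects are added for within-participant correlation. The only covariates are these: "Additionally, the model will include the stratification variables". The abstinence analysis identifies the stratification variable: "The model will also include stratification variables (gender) as recommended in the CPMP guidelines". The text does not say whether the enrollment BPI score is one of the repeated outcomes, and it does not say which of the listed tests decides the hypothesis.

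Baseline adjustment appears only under Data Summary, for characteristics found to be imbalanced: "we will consider sensitivity analyses adjusting for these baseline characteristics to ensure that an observed intervention effect is not due to this baseline imbalance".

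Enrollment pain is available, because the baseline survey covers "depression, pain intensity and other covariates related to pain and smoking, via telephone". For abstinence the plan does fix a time point: "We will use logistic regression to test for a between-group difference in abstinence rates at 6 months", with 12 months as sustainability. Pain has no such rule.

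**The concern.** A patient's pain score at enrollment usually predicts later pain. A model that ignores it leaves that predictable variation in the error term. A mixed model does not recover it automatically. With a free mean for each arm at each visit and complete data, the estimated 6-month difference is simply the difference in 6-month means, whether or not the enrollment score is an outcome row. The treatment-by-time contrast from enrollment is the change score. Neither reaches the precision of the baseline-adjusted difference.

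The lack of a named contrast adds to this, because the listed tests answer different questions:

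- **Enrollment is an outcome row.** The treatment main effect averages in a visit before treatment, and targets only two thirds of an effect that is equal at 6 and 12 months.
- **Enrollment is not a row.** The interaction asks only whether the effect differs between 6 and 12 months, so a constant benefit would look null.

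At stake are the power and clarity of the pain result.

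**Working it through.** The plan gives no sample size, SD, effect size or correlation for pain, so there is no stated figure to reproduce.

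**Inputs.** From the documents: three visits (enrollment, 6 and 12 months), the listed model terms, and entry at BPI pain intensity of 4 or more. Assumed: unit variance at each visit, equal correlation ρ = 0.3/0.5/0.7 between visits, equal allocation, complete data, two-sided 5% level. The common factor 4/N cancels from every ratio. Information kept = adjusted variance ÷ unadjusted variance.

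**6-month difference**

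| Contrast | Variance | ρ = 0.3 | 0.5 | 0.7 |
|---|---|---|---|---|
| Adjusted | 1−ρ² | 0.91 | 0.75 | 0.51 |
| Follow-up only | 1 | 1 | 1 | 1 |
| Change score | 2(1−ρ) | 1.40 | 1.00 | 0.60 |
| Kept, follow-up only | 1−ρ² | 91% | 75% | 51% |
| Kept, change score | (1+ρ)/2 | 65% | 75% | 85% |

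Power where the adjusted 6-month test has 80% is Φ(2.80·√kept − 1.96). This gives 76/68/52% for follow-up only and 62/68/73% for change. A simulation of 471 patients (the two site goals, 371 + 100) with 8,000 trials per ρ gave 75.8/67.3/51.9% and 61.9/68.0/73.4%. The mean estimates agreed across methods, so there is no bias.

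**Average of 6 and 12 months**

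| Contrast | Variance | ρ = 0.3 | 0.5 | 0.7 |
|---|---|---|---|---|
| Adjusted | (1+ρ)/2 − ρ² | 0.56 | 0.50 | 0.36 |
| Unadjusted level | (1+ρ)/2 | 0.65 | 0.75 | 0.85 |
| Mean change | (1+ρ)/2 + 1 − 2ρ | 1.05 | 0.75 | 0.45 |
| Kept, level | | 86% | 67% | 42% |
| Kept, mean change | | 53% | 67% | 80% |

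**Choice of contrast.** If the effect is equal at both visits, the adjusted 6-month difference carries 0.56/0.91, 0.50/0.75 and 0.36/0.51 of the information of the adjusted average, that is 62/67/71%.

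**Main effect over three visits.** Its variance is (1+2ρ)/3 and its expectation is 2/3 of the effect. Rescaled by 9/4, the variance is 1.20/1.50/1.80, which is 2.14/3.00/5.00 times that of the adjusted average.

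**12-minus-6 contrast.** Its variance is 2(1−ρ) with or without baseline, so adjustment does not help this contrast under equal correlation.

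**Sensitivity (6 months unless stated)**

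- *Entry threshold.* Suppose it halves the enrollment variance and leaves the slope at ρ. The adjusted variance stays 0.91/0.75/0.51. Follow-up variance is 1 − ρ²/2 = 0.955/0.875/0.755, so follow-up only keeps 95/86/68%. Change variance is 1−ρ² + (1−ρ)²/2 = 1.155/0.875/0.555, so change keeps 79/86/92%.
- *20% loss to follow-up, enrollment as a row.* The variance ratios to the adjusted contrast are 1.08/1.27/1.77 for level and 1.43/1.27/1.14 for change. With complete data they are 1.10/1.33/1.96 and 1.54/1.33/1.18.
- *Correlation with 12 months falling to ρ².* At 12 months follow-up only keeps 1−ρ⁴ = 99/94/76%, and change keeps (1+ρ²)/2 = 54.5/62.5/74.5%.

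**The case against.** The strongest reply is that the plan may already be adequate. If enrollment is not an outcome row, the listed treatment effect is the average of 6 and 12 months, which answers Goal 2 directly. If enrollment is a row, the two-degree-of-freedom interaction is a valid test of any difference in change. The entry threshold may weaken the correlation, and Data Summary allows adjusted sensitivity analyses. All of this is true, but it does not remove the loss: each level or change contrast remains less precise than its own adjusted version at every correlation examined. The sensitivity analyses are optional and triggered by imbalance, so they do not change the main test.

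A reader might infer that the adjusted 6-month difference must decide Hypothesis 2.1, as 6 months does for abstinence. The documents do not support that, because the goal names both visits equally. It could also do worse than the plan. The unadjusted two-visit average has variance 0.65/0.75/0.85 against 0.91/0.75/0.51 for the adjusted 6-month difference. Where the latter has 80% power, the former has 91/80/58% for an equal lasting effect.

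A reader might also take 75% at ρ = 0.5 as the typical loss. It is the least favourable point for the better of the two unadjusted 6-month contrasts, because their curves cross there. At 0.3 the better one keeps 91%, at 0.7 it keeps 85%, and under the assumed entry effect the value at 0.5 is 86%.

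**Conclusion.** The point holds as an improvement that should be made. The main pain model omits a strong candidate covariate that is already collected, and the deciding test is unnamed. For the two-visit average, the better of the unadjusted level and mean change keeps 86/67/80% of the adjusted information at ρ = 0.3/0.5/0.7, and the worse keeps 53/67/42%. These figures rest on assumed equal correlation and complete data. The documents give no correlation, and the entry threshold may make the loss smaller. The need to name the contrast does not depend on ρ.

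A reader might infer bias, or a threat to the trial's main result. Neither is supported. Under randomization the unadjusted contrasts are unbiased, and the main outcome is prolonged abstinence, which this model does not analyze. Nor does the plan say that it will decide on a main effect diluted by the enrollment visit. It only leaves that possible.

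**What to change.** For each BPI scale, make the 6- and 12-month scores the outcomes of the main model and add enrollment BPI and enrollment BPI-by-time as covariates. Keep group, time, group-by-time and gender. The equivalent model with enrollment as an outcome and a common baseline mean in both arms is also acceptable, provided its covariance lets enrollment relate freely to each follow-up visit.

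Name one baseline-adjusted follow-up contrast in advance, and report the adjusted differences at both 6 and 12 months. The adjusted average of the two visits fits Goal 2 and is at least as precise as the plan's unadjusted average. The adjusted 6-month difference is an alternative, at the price in information shown above. If enrollment stays as an outcome row, do not decide on a treatment main effect that includes it. If it is not a row, do not decide on the interaction.

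The cost is SAP wording and a few degrees of freedom, with no new visits or patients. One check is needed. The baseline survey list names pain intensity but not interference, while Outcome 3 says "Participants will complete the BPI, which includes 2 multi-item scales measuring pain intensity and pain-related functional interference". Confirm that the 7 interference items are recorded at enrollment.

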If there is a significant intervention effect on smoking cessation (i.e., if  $\beta_1$  is significantly different from zero in the first model above in Hypothesis 1.1), then we also plan to examine whether change in self-efficacy and pain-related anxiety mediate the impact of the intervention. This aim can be addressed under the general framework of mediation. We propose to conduct this mediation analysis using the MacArthur approach, a modification of the traditional Baron & Kenny criteria, developed for use specifically in randomized clinical trials. By the MacArthur definition, the potential mediator must be evident during or post-treatment; therefore, for example, the change in patient self-efficacy measures between baseline and 6-months will be considered as potential mediators. The outcome will be patients' abstinence at 12-months. We will first fit a model to examine the correlation between the mediator (C) and the SMK-CBI group:  $C = \gamma_0 + \gamma_1 * \text{SMK-CBI}$ . We also fit a model that examines the relationship between the mediator and the probability of abstinence (p):  $\text{logit}(p) = \beta_0 + \text{SMK-CBI} * \beta_1 + C * \beta_2 + C * \text{SMK-CBI} * \beta_3$ . Improvements in patient self-efficacy or pain-related anxiety will be considered to account for improvements in abstinence rates if there is evidence that  $\gamma_1$  is not equal to zero, and if either  $\beta_2$  or  $\beta_3$  are not equal to zero.

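### The Hypothesis 3.1 abstinence model uses a raw change score with no baseline mediator or baseline confounder, so its mediator slope is generally attenuated or confounded

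*Combined protocol and SAP*

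**What the plan says.** The place is the combined protocol and SAP, Section VI, Analyses, Hypothesis 3.1. If the intervention effect in the Hypothesis 1.1 model is significant, the plan will "examine whether change in self-efficacy and pain-related anxiety mediate the impact of the intervention". The example given of a mediator is "the change in patient self-efficacy measures between baseline and 6-months will be considered as potential mediators". On the outcome it says: "The outcome will be patients' abstinence at 12-months".

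Two models are written out.

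- Mediator model: "We will first fit a model to examine the correlation between the mediator (C) and the SMK-CBI group". It regresses C on arm only, with arm coefficient γ1.
- Abstinence model: the logit of the abstinence probability on arm (β1), C (β2) and C × arm (β3).

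Mediation is declared if γ1 differs from zero and either β2 or β3 differs from zero. No sign is required.

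No sentence in this part adds covariates. For Hypotheses 1 and 2, by contrast, sentences add the stratification variables to the models. The Data Summary paragraph only considers adjustment, as a sensitivity analysis for imbalance between arms. Section V lists variables collected at baseline, among them "smoking history, nicotine dependence, global self-efficacy to quit smoking, depression, pain intensity".

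**The concern.** Randomisation protects the comparison of arms. It does not protect the comparison of patients whose mediator changed much with patients whose mediator changed little. Two problems follow for the abstinence model.

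1. A change score tends to be negatively correlated with its own baseline. A Veteran who starts with high self-efficacy has little room to gain but may be more likely to quit. With the baseline level left out, its effect on abstinence is loaded onto C with the opposite sign.
2. Nicotine dependence, depression or pain could affect both the mediator and quitting. None of them is in the model.

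Mediation is one of the study's three stated goals, and its conclusion rests on the coefficients of C. A real mediator could be missed, or a false one declared.

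**Working it through.** **Inputs.** The documents give no power, effect size, abstinence rate, mediator SD, correlation or dropout figure for this analysis, so there is no stated figure to reproduce. The recruitment goals in Section 6 are 371 and 100, giving 371 + 100 = 471 if they add. Everything else is assumed: baseline mediator M0 and 6-month mediator M6 with equal SDs (set to 1) and correlation r of 0.3, 0.5 or 0.7; about 20% abstinence; log OR 0.4 per SD; arm effect on the mediator 0.25 SD; full retention; two-sided 5% tests.

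**Slope on C = M6 − M0.** Let the log-odds of abstinence depend on b·M6 + c·M0. On the linear scale, within arm:

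- Cov(M6, C)/Var(C) = (1 − r)/[2(1 − r)] = 0.5
- Cov(M0, C)/Var(C) = −(1 − r)/[2(1 − r)] = −0.5
- Slope on C ≈ 0.5(b − c), whatever r is

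| What drives abstinence | b | c | Slope on C |
|---|---|---|---|
| 6-month level | 0.4 | 0 | 0.20 |
| Both levels equally | 0.4 | 0.4 | 0 |
| Baseline level only (no mediation) | 0 | 0.4 | −0.20 |
| Change itself | 0.4 | −0.4 | 0.40 |

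The logit scale alters this little. In large simulated samples with b = 0.5 and c = 0, the model as written gave slopes of 0.24–0.25, and 0.49–0.51 once baseline was added.

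**Arm-to-mediator model.** Randomisation makes γ1 unbiased either way. The residual variance is 2(1 − r) for raw change and 1 − r² with baseline as covariate. At r = 0.5 these are 1.00 and 0.75:

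- Raw change: SE = √(4 × 1.00/471) = 0.092; 0.25/0.092 = 2.71; power ≈ Φ(2.71 − 1.96) ≈ 77%
- Adjusted: SE = √(4 × 0.75/471) = 0.080; 0.25/0.080 = 3.13; power ≈ Φ(3.13 − 1.96) ≈ 88%

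At r = 0.3 and 0.7 the pairs are 63% against 81%, and 93% against 97%.

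**Full written rule.** This was simulated with the arm × mediator term and the γ1 condition, but without the requirement of a significant Hypothesis 1.1 effect.

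| Truth | As written | 6-month value plus baseline |
|---|---|---|
| Real mediator, 6-month level, r = 0.3/0.5/0.7 | about 16/17/15% | about 44/47/44% |
| Change itself causal, r = 0.3/0.5/0.7 | about 45/44/37% | about 48/49/45% |
| Only baseline predicts quitting (no mediation) | about 15–18% | about 6–8% |

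The last entry exceeds 5% because either of two coefficients may trigger the rule. All entries carry simulation error of a few percentage points.

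**Baseline confounder.** This used a separate set of assumptions: 377 retained (0.8 × 471 ≈ 377), r = 0.5, abstinence 15–25%, arm effect 0.4 SD, and a confounder with loading 0.4 on the mediator and log OR 0.5 on abstinence. With no true mediation, the rule as written fires in 17–20% of trials. Adding only the baseline mediator gives 20–27%. Adding the confounder as well gives about 9%, against 7–8% where no confounder exists. Both kinds of adjustment are therefore needed.

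**The case against.** The plan names change as the mediator. If change is the causal quantity, the raw slope is unbiased, and adjustment costs power on the single mediator coefficient (93% raw against 84% adjusted at r = 0.5). This stands as a special case, but the documents give no reason to expect it. Even there, the adjusted version does no worse under the full rule.

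A reader might infer that false mediators would appear in up to half of trials. The coefficient on C alone, with no interaction term, is indeed significant in 52/40/26% of trials at r = 0.3/0.5/0.7 when only the baseline level matters. That is not the plan's test. Under the full rule the figure is about 15–18%. Requiring a significant arm effect as well brought it to about 7/7/5% in one run, which used the simulated outcome as a stand-in for the 6-month one. The slope in this case is negative: greater gain goes with less quitting. It counts only because the rule states no sign, although the plan's wording concerns improvements.

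A reader might also infer that both models are biased. They are not: the arm-to-mediator model loses precision only.

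Three further points have some force. The change score is introduced as an example for self-efficacy, but the section speaks of change in both mediators and uses one C. The Hypothesis 1.1 equation also leaves out gender, which is then added in words, so the equations may not be exhaustive; however, Hypothesis 3.1 has no such added sentence. Lastly, the named mediation approach cites sources that were not available for this review.

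**Conclusion.** The concern holds for the abstinence model. As written, the slope on C is generally attenuated or confounded, and it recovers the mediator effect only when change itself is causal and no confounder is omitted. The plan's general intention to consider adjusting for imbalance between arms does not deal with this.

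Under the stated assumptions, the chance of finding a real mediator that acts through its 6-month level is about one third of what the same data allow (about 15–17% against 44–47%). These sizes rest on assumed inputs and full retention. The direction of bias depends on b and c, so it would be wrong to say that the slope is always halved.

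The matter is confined to the third aim, which is examined only after a significant abstinence effect. It does not touch the abstinence or pain conclusions. It should be corrected, but it does not threaten the trial's main result.

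**What to change.** In the Hypothesis 3.1 text:

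- Replace C by the 6-month mediator value, with that mediator's baseline value as a covariate, in both models. Keep the arm × mediator term in the abstinence model.
- Add gender to both models.
- Add prespecified baseline nicotine dependence, depression and usual pain intensity to the abstinence model.
- Require the coefficients to have the signs consistent with mediation.
- State that the mediator–abstinence link is observational. It stays open to post-baseline confounding, notably by smoking status at the same 6-month survey: quitting by then could raise self-efficacy and also predict 12-month abstinence. Baseline covariates do not remove this.

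The cost is wording. The change score already needs both mediator values, and the covariates are collected at baseline. The abstinence model would have 8 coefficients besides the intercept: arm, mediator, their product, baseline mediator, gender and three confounders. At 20% of 471 there are about 94 events, or about 12 per coefficient. At 15% of 297 (80% of 371 retained) there are about 45, or between 5 and 6 per coefficient. The covariate list should therefore stay short. The other cost is some power on the single mediator coefficient if change itself is the causal quantity.
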